We estimated a pre-defined 8-point non-inferiority margin, based on a significant effect of the COGNI-TRAcK in inducing an about 8-point mean increase at SDMT score (with respect to a sham intervention). Accordingly, 35 subjects per arm are required to ensure, with an approximately 85%-power level, that the lower limit of a one-side 95% confidence interval will be above the pre-defined non-inferiority margin. Therefore, considering also a drop-out rate of 25%, a total of 132 subjects should be enrolled.

Statistical methods

All analysis will be based on the intention-to-treat principle using the fully analysis dataset including all randomized patients. Missing data will be handled by multiple imputation method. Continuous data will be analyzed by parametric and non-parametric RM-ANOVAs with effect size estimation. The time-to-event data will be analyzed by Kaplan-Meier curves and Log-Rank test with a factor for treatment group.

An interim analysis will be conducted when at least 50% of the estimated sample size will complete the 8-week intervention period.

Study objectives

Primary objective	Primary endpoint
To demonstrate not inferior efficacy of exergames over COGNI-TRAcK and superior efficacy of both interventions over sham in improving sustained attention and information processing speed	Change at the SDMT from baseline to Week 8
Secondary objectives	Secondary endpoints
To demonstrate not inferior efficacy of exergames over COGNI-TRAcK and superior efficacy of both interventions over sham in improving cognitive functions	Change at the BICAMS and SCWT from baseline to Week 8
Additional objectives	Additional endpoints
To demonstrate not inferior efficacy of exergames over COGNI-TRAcK and superior efficacy of both interventions over sham in reducing the impact of MS on: - cognitive-motor interference - activities of daily living - fatigue - work productivity	Change of dual-task cost of walking and balance as estimated by the 2MWT and static posturography in dual-task vs. single-task condition from baseline to Week 8 Change at the MSIS-29 from baseline to Week 8 Change at the MFIS from baseline to Week 8 Change at the WPAI:MS from baseline to Week 8
Exploratory objectives	Exploratory endpoints
To demonstrate not inferior efficacy of exergames over COGNI-TRAcK and superior efficacy of both interventions over sham on: - physical activity - adherence	Physical activity measured by wearable actigraph Percentage of training completed at home

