The blinding is ensured by using single-blind technique. A two-operator (treating and assessing) model is used to assist with study masking. The treating operator at each site is **not blind** to intervention arm and he/she is responsible for evaluating patient eligibility, for explaining how to use the devices and for recording and managing AEs. The assessing operator is an independent neuropsychologist or physiotherapist who is **blind** to intervention arm and he/she is exclusively responsible for on-study assessments.

Study discontinuation and drop-out

Patients who are screened for enrolment, but not randomized (e.g. because they do not fulfill eligibility criteria or do not provide a valid informed consent) will be considered as **screening failure** and their data will be not analyzed.

Patients are free to discontinue any intervention at any time, without prejudice to further treatment or care. A patient who decides to discontinue whatever training protocol will be considered as **drop-out** and he/she will always be asked about the reason(s) for discontinuation and the presence of any AE. Premature discontinuation of whatever training protocol does no impact on the patient's participation in the study, since the patient will always be asked to continue attending the subsequent study visit to ensure complete data for an intention-to-treat analysis.

If the patient does not agree to continue in-person study visits, he/she will be considered as **lost to follow-up** and a modified follow-up must be arranged via telephone contact to ensure at least the collection of safety information.

STUDY PLAN AND TIMING OF PROCEDURES

Visit	Week 0 Screening Randomization Baseline	Week 8 (+/- 5 days) Immediate post-training	Week 16 (+/- 5 days) Study Termination
Signed informed consent	X		
Eligibility criteria	X		
Demographic and clinical data collection (CRF)	X		
EDSS score	X		
BDI	X		
MMSE	X		
Randomization & study code assignment	X		
CRIQ	X		
HLAQ	X		
TCI	X		
BICAMS (including SDMT, CVLT2, BMVT-R)	X	X	X
SCWT	X	X	X
2MWT (single-task & dual-task)	X	X	X
Static posturography (single-task & dual-task)	X	X	X
MSIS-29	X	X	X
MFIS	X	X	X
WPAI:MS	X	X	X
Physical activity data collection (actigraph)		X	X
Check of adherence to intervention protocol		X	
Check of AEs		X	X
Device for intervention	Dispense	Return	
Patient diary	Dispense	Return	
Logbook	Dispense	Check	Return
Actigraph	Dispense	Check	Return

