Exploratory endpoints: the MSIS-29 is a self-administered questionnaire measuring physical and psychological impact of MS from the subject's perspective; it has been reported to be more sensitive than other quality of life scales in detecting rehabilitation-induced changes [43]. The MFIS-21 is a self-administered questionnaire based on items derived from interviews with subjects with MS concerning how fatigue impacts their lives; it comprises three subscales (physical, cognitive, and psychosocial functioning) [44]. The WPAI:MS questionnaire measures employment status, absenteeism, impairment during work, overall work impairment and daily activity impairment [45].

Adherence

All eligible patients will receive a logbook to daily record the log of training (including time and type of game played). The logbook will be given at baseline visit and will be returned to the treating operator at the end of the training period (Week 8 visit). The machine log included in all the devices used in the present study allows double-check of adherence to intervention protocol.

Safety

Patients will be encouraged to contact the treating operator or another component of the study team (excluding the assessing operator) in case of AEs, for any question regarding the study protocol or technical problems. All eligible patients will receive a patient diary to record any AE occurring during the study and the occurrence of accidental falls, defined as an unexpected contact of any part of the body with the ground that not results from loss of consciousness. The patient diary will be given at baseline visit and will be returned to the treating operator at the end of the follow-up period (Week 16 visit).

AEs will be reported according to the World Health Organization (WHO) guidelines for Good Clinical Practice (GCP) in biomedical research on human subjects [46]. AEs are graded as mild (minimal or no treatment required and no interference with daily living activities), moderate (may require treatment and cause some interference with functioning), severe (systemic drug or other treatment required, interruption of daily living activities), or life-threatening (immediate risk of death).

Predictors of outcomes

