No pharmacological treatment is strictly forbidden; however, patients are encouraged to not start pharmacological treatments that can potentially impact on cognition, namely antidepressants, dalfampridine, nabiximols, modafinil, amantadine, dopamine-agonists.

Steroid administration due to MS relapse or any symptomatic drug initiation due to any MS-related symptom should be considered as an AE.

Patients are encouraged to not start any other type of physiotherapy or rehabilitation during the study period, but they are encouraged to continue his/her physiotherapy or rehabilitation program if started at least 3 months before the study enrolment.

STATISTICAL PLAN

Sample size estimation

Overall, we will randomize **126 patients** (considering even a 20% drop-out rate), based on two previously published studies that have found:

- (i) a significant effect of an home-based cognitive training using the [name]® Brain Training that promoted an about 8-point mean increase at SDMT score (with respect to wait-list group) [53];
- (ii) a significant effect of adaptive COGNI-TRAcK that promoted an about 8-point mean increase at SDMT score (with respect to a sham intervention) [24];
- (iii) a 50%-difference in proportions of responders (10/14 versus 3/14 in adaptive COGNI-TRAcK group and sham COGNI-TRAcK group, respectively) [24], according to a responder definition of SDMT change approximating 4 points or 10% in magnitude [28].

For the non-inferiority comparison, the null hypothesis is that the intervention with exergames is inferior to adaptive COGNI-TRAcK, while the alternative hypothesis is that the intervention with exergames is non-inferior to adaptive COGNI-TRAcK by a pre-defined amount of SMDT score.

If there is truly no difference between exergames and adaptive COGNI-TRAcK, then 35 patients per arm are required to ensure, with a statistical power of approximately 85%, that the lower limit of a one-sided 95% confidence interval (or equivalently a 90% two-sided confidence interval) will be above the predefined non-inferiority margin of 8-point change in SDMT.

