For the superiority comparison, the null hypothesis is that the intervention with adaptive COGNI-TRAcK is not superior to sham COGNI-TRAcK, while the alternative hypothesis is that the intervention with adaptive COGNI-TRAcK is superior to sham COGNI-TRAcK in increasing the proportion of responders as afore defined. Enrolling 35 patient per arm will ensure a more than 95% power in detecting a statistical significance between-group difference of 50% at two-sided alpha level of 5%.

Statistical analysis

All analysis will be based on the intention-to-treat principle using the fully analysis dataset including all randomized patients. Missing data will be handled by multiple imputation method, with the assumption that some data will be missed completely at random.

Efficacy analyses: efficacy data will be analyzed by parametric and/or non-parametric Repeated Measures Analyses of the Variance (RM-ANOVAs) with effect size estimation. In each analysis, we will consider as dependent variable all measures or score derived from study assessments; the three study visits (Baseline, Week 8 and Week 16) as within-subject factors; and intervention arms (exergames, adaptive COGNI-TRAcK and sham COGNI-TRAcK) as between-subject factors. Effect sizes will be estimated as Cohen's F-squared, rated as small, medium, and large for values of 0.02, 0.15, and 0.35, respectively [54].

Safety data regarding time to first accidental falls will be analyzed as time-to-event data by Kaplan-Meier curves and Log-Rank test with a factor for intervention arms.

Safety analyses: data regarding the occurrence of adverse events during the intervention period and the follow-up period will be analyzed by the Chi-squared test comparing the independent distribution of events according to intervention arms.

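### The non-inferiority claim rests on the all-randomised set alone, where training stopped in both active arms can hide a deficit of exergames; separately, the completely-at-random assumption is implausible

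*Protocol*

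**What the plan says.** The protocol's Statistical analysis section states: "All analysis will be based on the intention-to-treat principle using the fully analysis dataset including all randomized patients". The synopsis repeats this. Nothing exempts the non-inferiority comparison, which is part of the primary objective and drives the 35 patients per arm. The non-inferiority test asks that the lower one-sided 95% confidence limit lie "above the predefined non-inferiority margin of 8-point change in SDMT". The same section adds: "Missing data will be handled by multiple imputation method, with the assumption that some data will be missed completely at random".

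Under Study discontinuation and drop-out, the label of drop-out is attached to stopping the training, not to leaving the visits: "A patient who decides to discontinue whatever training protocol will be considered as" a drop-out. Such patients stay in: "Premature discontinuation of whatever training protocol does no impact on the patient's participation in the study", and "the patient will always be asked to continue attending the subsequent study visit to ensure complete data for an intention-to-treat analysis". The planned drop-out rate is 20% in the Sample size estimation section (126 patients) and 25% in the synopsis (132 patients).

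Adherence is well measured. Patients keep a daily logbook, and "The machine log included in all the devices used in the present study allows double-check of adherence to intervention protocol". The Interventions section sets 40 sessions. In the table of objectives, however, "Percentage of training completed at home" is only an exploratory endpoint. The protocol names no per-protocol or adherence-based set and no sensitivity analysis for the non-inferiority comparison.

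**The concern.** In a superiority comparison, patients who stop treatment but stay in the analysis usually pull the estimate towards zero, which is conservative. In a non-inferiority comparison a pull towards zero can help the claim. Here the protocol itself foresees a sizeable share of stoppers, asks them to stay in the data, and provides no second analysis that would show whether similarity of the arms reflects similar training effects or training that was not done.

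The margin makes this matter more. The 8 points equal the whole effect of adaptive over sham COGNI-TRAcK that the protocol cites. Exergames sitting at the margin would therefore do no better than sham among those who train.

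The missing-data assumption is a second issue. Stopping home training, and later missing a visit, will plausibly relate to arm, adherence, adverse events and disability. The Predictors of outcomes section itself sets out to explore whether personality and pre-morbid reserve predict both adherence and the size of the effect. That sits badly with data missing completely at random.

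**Working it through.** **Inputs.** From the protocol: margin 8 SDMT points; one-sided 5%; power about 85%; true difference 0; 35 per arm; drop-out 20% or 25%; cited adaptive-versus-sham effect about 8 points. Not in the protocol: the SD of the SDMT change.

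**The plan's own figure.** With no SD, 35 per arm cannot be reproduced independently. It can be inverted:

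SD = 8 × √(35/2) / (1.645 + 1.036) = 8 × 4.183 / 2.681 ≈ 12.48.

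The same formula gives 23 per arm at SD 10 and 51 per arm at SD 15. I use 12.48 as the assumption and show 10 to 15 as the range.

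**Number analysed.** If stoppers stay in, the relevant size is the number randomised: 126/3 = 42 or 132/3 = 44 per arm (105 × 1.20 = 126; 105 × 1.25 = 131.25, rounded up to 132).

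**Dilution.** Assume a share q of each active arm stops training, stoppers do not differ between arms, and those who train have a true deficit of 8. Then:

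- all-randomised deficit = 8 × (1 − q), which is 6.4 at q = 20% and 6.0 at q = 25%;
- P(non-inferiority declared) = Φ[(8 − deficit) / (SD × √(2/n)) − 1.645].

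For n = 42 and q = 20%: SD × √(2/n) = 12.48 × 0.2182 = 2.723; 1.6/2.723 − 1.645 = −1.057; Φ = 14.5%.

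For n = 44 and q = 25%: 12.48 × 0.2132 = 2.661; 2.0/2.661 − 1.645 = −0.893; Φ = 18.6%.

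| n per arm | q | SD 10 | SD 12.48 | SD 15 |
|---|---|---|---|---|
| 42 | 0% | 5.0% | 5.0% | 5.0% |
| 42 | 20% | 18.1% | 14.5% | 12.4% |
| 44 | 25% | 24.0% | 18.6% | 15.4% |

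**Opposite pattern.** If the arms are truly equal on training and only exergames patients stop, losing the 8-point gain, the all-randomised deficit is 8 × 0.20 = 1.6 or 8 × 0.25 = 2.0. At 42 per arm and SD 12.48, power falls from 90% to 76% or 71%. The all-randomised analysis then works against non-inferiority.

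**Does the imputation cause the dilution?** A simulation (44 per arm, SD 12.48, exergames gain 0, adaptive gain 8, stoppers' gain 0, 4,000 runs, 20 imputations) separates the two mechanisms:

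| Handling of stoppers | Mean deficit, q = 20% / 25% | Non-inferiority declared, q = 20% / 25% |
|---|---|---|
| Kept with observed data | 6.37 / 6.01 | 15.4% / 18.7% |
| Missing, imputed within arm | 8.03 / 8.04 | 4.9% / 4.8% |
| Missing, imputed ignoring arm | 6.39 / 6.00 | 9.0% / 10.5% |

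The dilution comes from stoppers who are observed and kept. Imputation adds to it only if the imputation model leaves out arm, and the protocol does not say that it does.

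**The case against.** Several stronger readings are tempting, and the document does not support them.

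- **That the completely-at-random assumption produces the false claim.** It does not: imputation within arm keeps the rate near 5%. The protocol also says only that some data are missing in this way, gives no imputation model and excludes no predictor. Details of the model may properly sit in an analysis plan that is not shown. What can be criticised is the assumption that the protocol does state.
- **That poor adherence necessarily favours non-inferiority.** The direction depends on who stops, as the opposite pattern shows.
- **That the planned test has an inflated type I error.** For the effect in all randomised patients, a deficit of 6.0-6.4 points really is inside the margin of 8. The 14-19% is an error rate only for the effect among those who train. For a home programme, the effect as actually used is a legitimate target, so this is no reason to demand success in both sets as a condition of the primary claim.
- **That the risk is far larger.** Back-solving an SD from the cited responder shares (10/14 and 3/14) and the 8-point difference, under normality and equal SDs, gives 8/(0.566 + 0.792) ≈ 5.9. With 35 per arm this yields 30-41%. But at SD 5.9, 35 per arm would have power above 99.9%, not about 85%. Moreover, 35 is the number left after drop-outs are removed, so it should not be diluted again.

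The protocol also works against the problem: it asks stoppers to keep attending, plans phone contact every two weeks to encourage training, and checks adherence in two ways. These measures reduce stopping or missing data. They do not supply the missing check on the non-inferiority conclusion.

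**Conclusion.** The point holds in a limited form. By its own wording the protocol ties the non-inferiority comparison to one analysis set in which stoppers are retained, and plans no adherence-based analysis beside it. If training is stopped in both active arms, that set can make exergames look closer to adaptive COGNI-TRAcK than they are among those who train: about 14-19% declarations of non-inferiority at a true on-training deficit of 8, against 5%.

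This size rests on four assumptions: an SD of about 12.5 (12-24% over SD 10 to 15 for the two designs shown); equal stopping in both arms; no difference between stoppers; and the planned 20-25% being the share that stops training, as the protocol's definition of drop-out implies. If that rate instead means patients with no Week 8 score, this dilution does not arise from them and the imputation matters more.

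The completely-at-random assumption is a separate weakness. It is implausible here and stronger than multiple imputation needs. It should be changed, but not because it causes the dilution.

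**What to change.** 1. Keep the all-randomised analysis as primary.
2. Add a pre-specified per-protocol analysis of the non-inferiority comparison. Define the set from the device logs as a stated share of the 40 sessions, and fix it before unblinding and before the planned interim analysis. Report it beside the primary analysis, and call the non-inferiority conclusion robust only if the two agree.
3. Replace the completely-at-random statement with multiple imputation under missing at random, with arm, baseline SDMT, EDSS, sessions completed and discontinuation of training in the model.
4. Add one delta-adjusted sensitivity analysis that worsens imputed exergames values.

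The cost is wording and some extra analysis; the data are already collected. The drawback is that the per-protocol set is smaller and not fully protected by randomisation, since those who keep training may differ between arms. It is therefore supportive and does not replace the primary analysis.

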
Rationale for study design and duration

This is a multi-centre, 16-week (8-week intervention followed by 8-week follow-up), randomized, single-blind, parallel-arm study comparing three different types of home-based training:

- (1) active video games of balance delivered by the Wii balance board, from here onwards called **‘exergames’** (intervention of interest);
- (2) Cognitive Training Kit (COGNI-TRAcK) with increasing difficulty levels, from here onwards called **‘adaptive COGNI-TRAcK’** (comparator intervention);
- (3) COGNI-TRAcK at constant difficulty level, from here onwards called **‘sham COGNI-TRAcK’** (placebo-analogue intervention) [24].

This study design will allow us to test the hypotheses that (i) exergames and adaptive COGNI-TRAcK are more effective than sham adaptive COGNI-TRAcK; (ii) exergames are not inferior to adaptive COGNI-TRAcK.

The choice of an 8-week study duration was based on previously published papers on cognitive training delivered by COGNI-TRAcK. In this study, 8 weeks of adaptive COGNI-TRAcK training were sufficient to determine a significant improvement in the SDMT score when compared with sham COGNI-TRAcK, yielding to a post-training between-arm difference of 8 points ($p < 0.001$) [24].

The 8-week post-training follow-up period will allow us to investigate the retention of training effect, which is an underinvestigated topic in MS rehabilitation setting. Literature data provide conflicting results (no retention for exergames, 6-month retention for cognitive rehabilitation) [9],[24].

Rationale for interventions

Exergames (the portmanteaux for “exercise” and “video games”) represent a form of whole-body physical exercise performed through active video games. Playing exergames involves not only the hand-eye coordination, but also whole body physical exertion, with the aim of improving fitness and promoting an active lifestyle [8]. Unlike the fully immersive VR (that simulates a lifelike multisensorial experience in a 3-dimensional artificial environment), the non-immersive VR involves the use of smaller-scale, 2-dimensional environment (e.g. home TV, computer display, etc) and interface devices, such as balance board, motion controllers or cameras equipped with depth sensors that can also provide haptic or kinesthetic communication reproducing tactile sensations by applying forces, vibrations or motions [7].

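### The primary endpoint is SDMT change at Week 8, but the only stated efficacy analysis is a three-visit RM-ANOVA with no Week 8 contrast and no decisive term named

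*Protocol*

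**What the plan says.** The Protocol Synopsis (Study objectives) gives the primary endpoint as "Change at the SDMT from baseline to Week 8". The primary objective has two parts: exergames not inferior to adaptive COGNI-TRAcK, and both superior to sham.

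The section Rationale for study design and duration explains why there is a second post-baseline visit: "The 8-week post-training follow-up period will allow us to investigate the retention of training effect".

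The Statistical analysis section then states that "efficacy data will be analyzed by parametric and/or non-parametric Repeated Measures Analyses of the Variance (RM-ANOVAs) with effect size estimation". The model takes "the three study visits (Baseline, Week 8 and Week 16) as within-subject factors" and "intervention arms (exergames, adaptive COGNI-TRAcK and sham COGNI-TRAcK) as between-subject factors". It is the same for every outcome: "In each analysis, we will consider as dependent variable all measures or score derived from study assessments".

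That paragraph does not say whether the arm term, the arm-by-visit term or a particular contrast answers the primary question. The section on the pre-planned significance level sets a two-sided 0.025 because two arms are compared with sham; it does not mention visits. A confidence limit for exergames against adaptive COGNI-TRAcK, and a comparison of responder proportions for superiority, appear under Sample size estimation. Neither is carried into the efficacy analysis. An ANCOVA on the immediate post-training score is planned, but only for predictors of outcome.

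**The concern.** The endpoint concerns one interval, baseline to Week 8. The stated model has three visits, and its natural test of treatment, the arm-by-visit interaction, responds to any difference in the arms' profiles, including one that arises only after training has ended. Because no deciding contrast is named, a significant interaction could be reported as a result on the primary endpoint when the arms differ only in retention. A real Week 8 effect could also be harder to detect if it partly fades by Week 16.

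The non-inferiority part raises a separate problem. It needs a one-sided limit for a signed difference at Week 8, set against a margin. An F test has neither sign nor margin: a non-significant result does not show non-inferiority, and a significant one does not rule it out.

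**Working it through.** **Inputs from the protocol.** 35 per arm, about 85% power, one-sided 5% and a margin of 8 points (Sample size estimation); two-sided level 0.025 (Pre-planned statistical significance level); an effect of about 8 SDMT points for adaptive COGNI-TRAcK against sham (Sample size estimation).

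**Assumptions not in the protocol.** The SD of change, and equal correlation between visits. Under equal correlation the within-subject error variance is SD²/2.

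**The plan's own figures.** For superiority, responder rates of 10/14 and 3/14 with 35 per arm at two-sided 5% give 99.5% power, consistent with the stated figure of more than 95%. For non-inferiority no SD is given, so the figure can only be inverted. In the normal approximation, SD = 8 × √(35/2) / (1.645 + 1.036) = 12.48. With the t distribution on 68 degrees of freedom it is 12.36, the value used below. Then SD²/2 = 152.77/2 = 76.38.

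**Method.** For two arms with between-arm differences d at the three visits, the interaction noncentrality is λ = 35 × ½ Σ(d − mean d)² / (SD²/2). The test has 2 and 136 degrees of freedom and a critical F of 3.79 at 0.025.

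**1. Equal at Week 8, different retention.** Both arms gain 8 points by Week 8; one keeps the gain and the other loses it.
- d = (0, 0, 8), mean 2.67, sum of squares 42.67, half of it 21.33.
- λ = 35 × 21.33 / 76.38 = 9.78, so the interaction is significant in 71% of trials.
- A 5,000-run simulation at SD 12.5 and visit correlation 0.7 gave 68%, against 2.1% for a direct test of the Week 8 change.
- If the second arm keeps half its gain, d = (0, 0, 4), λ = 2.44 and the figure is 18%.

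**2. Power for a real 8-point Week 8 effect against sham.**

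| Pattern | d | λ | Interaction | Week 8 contrast |
|---|---|---|---|---|
| Fully kept | (0, 8, 8) | 9.78 | 71% | 66% |
| Fully lost | (0, 8, 0) | 9.78 | 71% | 66% |
| Half kept | (0, 8, 4) | 35 × 16 / 76.38 = 7.33 | 56% | 66% |

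The Week 8 contrast is a t test with noncentrality 8 / (12.36 × √(2/35)) = 2.71, 68 degrees of freedom and critical value 2.29. Its power does not depend on Week 16.

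**3. Sensitivity to the SD.** Take an SD of change of 7.75 (a visit SD of 10 and correlation 0.7: 10 × √0.6). SD²/2 = 30.03. Case 1 then gives λ = 35 × 21.33 / 30.03 = 24.9 and 99% of trials significant. With half the gain kept, power is 95% for the interaction and 98% for the Week 8 contrast. A smaller SD therefore makes the false signal more frequent and the power loss smaller.

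**The case against.** The strongest reply is that the model already contains what is needed. Visit is a factor with three levels, so a baseline-to-Week 8 contrast between arms can be taken from it, and training effect and retention can be estimated separately. The significance section points to two comparisons with sham rather than one pooled test, and naming contrasts is often left to an SAP. The first part stands: a reader might infer that the plan cannot test its primary endpoint or cannot separate effect from retention, and the protocol does not support that. What remains is that the protocol fixes the model and the visits and leaves the primary test open. The reference to sham comparisons does not say at which visit they are made.

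Other stronger readings also fail:
- **Severe dilution through the arm main effect.** That term averages over baseline and would have very low power, but the protocol never selects it.
- **An expectation that retention differs by arm.** The wording "no retention for exergames, 6-month retention for cognitive rehabilitation" summarises literature that the same sentence calls conflicting. The pattern in case 1 is therefore a possibility the protocol itself raises, not its forecast.
- **Inflated error from unequal visit correlations.** The protocol does not say the F test is uncorrected, so this cannot be charged against it.
- **Cohen's f-squared as a faulty criterion.** It is a supplementary effect size and no decision rule uses it.

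It is also fair to say that the exergames-adaptive comparison in case 1 is tied to a confidence limit in the sample size section. But that limit is not part of the stated efficacy analysis.

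**Conclusion.** The point holds as a mismatch between a Week 8 endpoint and an analysis that does not isolate Week 8. If the arm-by-visit test decides, arms that are equal at Week 8 and differ by 8 points in retention are declared different in about 71% of trials, falling to about 18% if retention differs by 4 points. Loss of power for a true Week 8 effect is conditional: about 56% against 66% with half the gain retained, and none if it is fully kept or fully lost. These figures rest on 35 per arm, level 0.025, equal visit correlations and an SD of change of 12.36 inferred from the sample size statement. The non-inferiority gap needs no such assumption: the efficacy analysis as written has no step that compares a Week 8 difference with the margin.

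**What to change.** In the Statistical analysis section, state that the primary hypotheses are tested by pre-specified Week 8 between-arm contrasts of SDMT change. These are each active arm against sham for superiority, and exergames minus adaptive COGNI-TRAcK by its confidence limit against the margin. Say whether they come from the repeated-measures model or from a baseline-adjusted Week 8 analysis, and report them in SDMT points with confidence intervals. Make the Week 16 contrasts a separate retention analysis. Settle this before the planned interim analysis.

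The cost is wording only: no extra data, visits or patients. If the gain is fully kept or fully lost at Week 16, the Week 8 contrast has slightly less power than the pooled interaction (66% against 71% pairwise, under the assumptions above).
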